Sphenopalatine Ganglion Block for PostDural Puncture Headache in Obstetric Postpartum Patients

Protocol: 16-1596

NCT: 02962427

Date: 10/26/2016

Protocol Synopsis Sheet

Below is the format to follow for the concept sheet for protocols. The point of a synopsis is that the critical elements of the protocol are summarized in a succinct manner. Bulleted or numbered lists should be used wherever possible.

Please limit your protocol concept sheet synopsis to four-to-five (4 - 5) pages (using 11-point Arial or 12-point Times New Roman typeface with one-inch margins). Please include your biosketch in the NIH format.

SYNOPSIS

Title of Study: Sphenopalatine Ganglion Block for PostDural Puncture Headache in Obstetric Postpartum Patients
Sponsor: None
Investigators: [name] MD MS, [name] MD, [name] MD PhD
Research Mentor: None
Study Center(s): University of Colorado Hospital
Clinical Phase (I, II, III)
Hypothesis: Sphenopalatine Ganglion Block is as effective as epidural blood patch for relieving post-dural puncture headache pain in postpartum obstetric patients
Aims: Specific Primary Aim: Compare the effectiveness of a sphenopalatine ganglion block to an epidural blood patch for postdural puncture headache relief in randomized postpartum parturients over a 48 period. Specific Secondary Aim: Compare the effectiveness of a sphenopalatine ganglion block in known versus unknown dural puncture for postdural puncture headache relief in randomized postpartum parturients over a 48 period.
Primary Objective(s): Compare pain scores after sphenopalatine ganglion block or epidural blood patch for postdural puncture headache treatment in postpartum parturients.
Secondary Objective(s): Evaluate effectiveness of sphenopalatine ganglion block and epidural blood patch for known and unknown dural puncture in postpartum parturients with PDPH.
Exploratory Objective (s): To determine if a minimally invasive technique (sphenopalatine ganglion block) is as effective in treating post-dural puncture headache in postpartum parturients as an invasive technique (epidural blood patch)
Study Design/Methods: After approval by the Institutional Review Board and completion of informed patient consent, we will include obstetric postpartum parturients presenting with a diagnosis of post-dural puncture headache (PDPH) as defined by the International Classification of Headache Disorders. These are both procedures utilized for the treatment of post-dural puncture headaches on the labor and delivery floor currently. Each study participant will be randomized to receive either an EBP or a SPGB; however, if the SPGB or EBP fails initially or subsequent failure within the 48 hour time period, the participant will be offered another SPGB or an EBP if in the SPGB arm or simply another EBP if in the EBP arm.

Maximum of 2 SPGB or EBP per patient.
 
We will also collect patient age, gravity, parity, BMI, ASA status, history of any headaches including migraines during or prior to pregnancy, details and timing of the original neuraxial procedure, delivery mode and details and other interventions attempted to relieve the headache (including repeated SPGB or EBP within 48 hours). We will document resolution of headache at 1 hour, 24 hours and 48 hours after procedure utilizing NRS scores (1-10). All documentation will be stored and accessed in our electronic medical record (Epic®).

Study Period: 7/1/2016 – 7/1/2019

Study Population: Postpartum obstetric parturients diagnosed with a post-dural puncture headache.

Number of Patients: 100 patients over a three year period

Timeline:
 
5/1/2016: Submission of IRB protocol
 
7/1/2016: IRB approval and beginning of enrollment of study subjects
 
7/1/2019: Completion of study
 
7/1/2019-9/1/2019: Completion of publication for submission


Main Criteria for Inclusion/Exclusion:
 
Inclusion Criteria:
 
 1) Age 18 years or age or greater postpartum obstetric parturient 2) Diagnosis of post-dural puncture headache based on the International Classification of Headache Disorders: 
 a. Any headache fulfilling criterion c b. Dural puncture has been performed c. Headache has developed within 5 days of the dural puncture d. Not better accounted for by another ICHD-3 diagnosis. e. Occurring immediately or within seconds of assuming an upright position and resolving quickly (within 1 minute) after lying horizontally. 
Exclusion criteria:
 
 1) Refusal to participate in the study 2) Non-english speaking 3) Placement of an EBP within the past 5 days 4) Allergy and/or intolerance to any the study materials 5) Contraindications to an EBP 6) Plan for therapeutic anticoagulation post-partum 7) Intolerance of at least 15mL of autologous blood via epidural or intolerance of the placement of the nasal swabs for 30 minutes 8) EBP less than 24 hour from neuraxial procedure/dural puncture

Data and Safety Monitoring Plan: The Principal Investigator (PI) will be responsible for the conduct of this study, including the blood sample handling and use, overseeing participant safety, executing the DSM plan, and complying with all reporting requirements to local and federal authorities. This oversight will be accomplished through additional oversight from the Data and Safety Monitoring Committee (DSMC) at the University of Colorado. The DSMC is responsible for ensuring data quality and patient safety for all clinical studies at the University of Colorado. A summary of the DSMC's activities is as follows:

- Conduct of internal audits
- Ongoing review of all serious adverse events (SAEs), unanticipated problems (UAPs) and reportable adverse events (AEs)
- Supervises internal DSM boards and/or performs as an internal DSMB (if requested)
- Has the authority to close and/or suspend studies for safety or conduct issues
- May submit recommendations for corrective actions to the Executive Committee

Per the DSM Plan, SAEs, UAPs and reportable AEs are reported to the DSMC, IRB and the sponsor per study protocol. All SAEs, UAPs and reportable AEs are to be reported to the DSMC within 5 business days of receiving notification of the occurrence.

Audits will consist of a review of the regulatory documents, consent forms, and source data verification. Results and recommendations from audits will then need to be submitted by the PI to the IRB of record at the time of the continuing review.

Risks to Patients: These are both procedures utilized for the treatment of post-dural puncture headaches on the labor and delivery floor currently.

Epidural blood patch: Common side effects include tenderness at site of injection and pressure in the lumbar spine. Rare risks include bleeding, infection, nerve damage, paralysis, dural puncture, no relief of symptoms.

Sphenopalatine ganglion block: Common risk is failure to relieve symptoms. Rare risks are damage to intranasal tissue or structures, anosmia or allergic reaction to medication.

Statistical Methods: There is a paucity of data in the literature evaluating the effect of EBP and SNB on PDPH pain using a numerical rating scale (NRS) or a visual analog scale (VAS). Most studies report outcomes in terms of complete, partial, or no relief. One study in 108 emergency department patients found that the correlation between a 10-point NRS scale and a VAS was 0.94 (95% CI 0.93-0.95), indicating that a verbally administered NRS can be substituted for the VAS in acute pain management. From our review of the few studies reporting NRS or VAS data, the baseline NRS or VAS in patients with PDPH is about 8-9 with a standard deviation of ± 1.5 , which might be reduced to about $3-4 \pm 3$ 1-6 hours after treatment, and perhaps to $1-2 \pm 1.5$ 24-48 hours after treatment. Assuming that we wish to detect a 1-2 unit difference in the NRS between the 2 treatment groups as being clinically meaningful, we calculate that we will need to randomize about $n = 100$ patients (50 patients in each treatment group) to achieve a statistical power of 90% for the trial.

The study data will be entered into REDCAP. Frequency distributions will be calculated for all variables to determine if the distributions of values look reasonable and if there are any outliers in the data. Suspected outliers will be corrected if needed, or truncated, or recoded as missing. Distributions will be tested for a normal (Gaussian) distribution. The primary statistical analysis will be by intention-to-treat. Treatment groups will be compared on demographic and clinical characteristics at baseline (Table 1). A CONSORT diagram will be prepared to describe screening and entry of patients into the clinical trial, and disposition of all patients after randomization. NRS means and standard deviations will be calculated for each treatment group at baseline, and 1, 24, and 48 hours after treatment. These mean values between the 2 treatment groups over time will be tested for statistical significance using a longitudinal mixed linear model. Side effects, adverse effects, and serious adverse effects will be recorded and compared for

each treatment group. Publication of results will follow the CONSORT 2010 checklist.

Funding/Budget: Funding for the statistical analysis will be requested from the Department of Anesthesiology. All treatments and supplies are currently employed on the labor and delivery deck, no additional funding is needed.

Requested Departmental Support: Funding for the statistical analysis will be requested from the Department of Anesthesiology. All treatments and supplies are currently employed on the labor and delivery deck, no additional funding is needed.

Expected Outcomes: After completion of this study, we will be able to determine the effectiveness of SPGB for the treatment of PDPH when compared to EBP placement. If SPGB are effective, this could change the management and algorithm in the treatment of PDPH for postpartum parturients.

Please include your biosketch in the NIH format (follow link below)

<http://www.google.com/url?sa=t&rct=j&q=&esrc=s&source=web&cd=3&ved=0CDoQFjAC&url=http%3A%2F%2Fgrants.nih.gov%2Fgrants%2Ffunding%2Fphs398%2Fbiosketchsample.doc&ei=wMbxUo-hD8b4yAHd-4GADw&usq=AFQjCNE4b9iv7E-afLxtF7fDYQvH9U-Pcg&bvm=bv.60799247,d.aWc&cad=rja>

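### The hypothesis claims SPGB is as effective as EBP, but the trial is sized and tested for a difference with no margin or confidence-interval rule, so a non-significant result cannot support it

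*Combined protocol and SAP*

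**What the plan says.** The Hypothesis entry in the synopsis reads "Sphenopalatine Ganglion Block is as effective as epidural blood patch for relieving post-dural puncture headache pain". It is the only hypothesis in the document. The Exploratory Objective repeats the idea, asking whether the block "is as effective in treating post-dural puncture headache in postpartum parturients as an invasive technique".

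The Primary Objective is neutral: "Compare pain scores after sphenopalatine ganglion block or epidural blood patch for postdural puncture headache treatment in postpartum parturients". Expected Outcomes is also neutral at first ("we will be able to determine the effectiveness of SPGB for the treatment of PDPH when compared to EBP placement"), then looks to practice: "If SPGB are effective, this could change the management and algorithm in the treatment of PDPH for postpartum parturients".

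Statistical Methods bases the sample size on a difference: "Assuming that we wish to detect a 1-2 unit difference in the NRS between the 2 treatment groups as being clinically meaningful". It arrives at about 100 patients, 50 per arm, for 90% power. The efficacy analysis, by intention-to-treat, is: "These mean values between the 2 treatment groups over time will be tested for statistical significance using a longitudinal mixed linear model". Alpha and sidedness are not stated. The only confidence interval in the document belongs to a cited NRS-VAS correlation.

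Under Study Design/Methods, if the first treatment fails within 48 hours, "the participant will be offered another SPGB or an EBP if in the SPGB arm".

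**The concern.** A test of no difference can reject equality but cannot establish it. A non-significant result means only that the data are compatible with zero. They may equally be compatible with a deficit that the plan itself calls clinically meaningful.

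If the hypothesis is true, non-significance is the expected result, and that is the result the plan gives no way to interpret. A significant SPGB advantage would support the hypothesis if it is read as *not worse*, but the trial is not planned to show one. With truly equal arms it would occur by chance in 2.5% of trials.

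The stakes are practical, since the investigators expect the result could alter how PDPH is managed. A margin chosen after the data are seen would not control the error rate.

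**Working it through.** **Inputs.** From Statistical Methods: 50 per arm; SD 3 at 1-6 h and 1.5 at 24-48 h; difference of interest 1-2 units; power 90%. Assumed: two-sided alpha 0.05, no dropout, and a two-sample t comparison at a single time point. The last stands in for the mixed model because no within-patient correlation is given.

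**Step 1: reproduce the plan's N.** Per arm, n = 2(z₀.₉₇₅ + z₀.₉₀)² / (Δ/SD)². With Δ/SD = 1/1.5 = 2/3, n = 2 × (1.960 + 1.282)² × 2.25 ≈ 47.3, so 48 per arm (96 in total). The t-test version gives 49 per arm (98 in total), and 50 per arm gives 91.0% power. The plan's 100 is therefore a difference-test size, with Δ = 1 at SD 1.5 or Δ = 2 at SD 3.

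**Step 2: precision.** The standard error is SD × √(2/50) = 0.2 × SD, that is 0.30 at SD 1.5 and 0.60 at SD 3. The 95% CI half-width (t = 1.984 on 98 df) is 0.595 and 1.191 units. At SD 3 a non-significant interval can extend past 1 unit even when the observed difference is zero.

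**Step 3: how often is a real SPGB deficit non-significant?** Noncentral t:

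| True deficit (units) | SD 3 (1-6 h) | SD 1.5 (24-48 h) |
|---|---|---|
| 1 | 62% | 9% |
| 1.5 | 30% | 0.1% |
| 2 | 9% | <0.1% |

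A rule requiring the upper 95% limit to lie below a margin equal to the true deficit would wrongly conclude equal effectiveness in 2.5% of trials in every cell.

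**Step 4: how often would the result be uninterpretable if the arms are equal?** This is the probability, at true difference 0, of a non-significant result whose 95% CI still reaches the margin (simulation, 1,000,000 trials):

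| Margin | SD 3 | SD 1.5 |
|---|---|---|
| 1 | 60% | 6.5% |
| 1.5 | 28% | <0.1% |
| 2 | 6.5% | <0.1% |

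Check for SD 3, margin 1: 1 − 0.378 (non-inferiority shown, Step 5) − 0.025 (EBP significantly better) = 0.597.

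**Step 5: what can 100 patients show under a margin rule?** Non-inferiority power with one-sided 0.025 and true difference 0:

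| SD | Margin 1 | Margin 1.5 | Margin 2 |
|---|---|---|---|
| 1.5 | 91% | 99.9% | >99.9% |
| 2 | 70% | 96% | 99.9% |
| 2.5 | 51% | 84% | 98% |
| 3 | 38% | 70% | 91% |

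If SPGB is truly 0.25 units worse, the 91% figures fall to 70% (margin 1, SD 1.5) and 82% (margin 2, SD 3). With 10% or 20% dropout (45 or 40 per arm) they fall to 88% or 84%.

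**The case against.** The strongest reply is that the primary aim and objective only ask for a comparison, which the planned test delivers, and nothing in the plan says non-significance will be read as equal effectiveness. This stands, and it confines the fault to the hypothesis and the exploratory objective. It does not remove the fault: this is the only stated hypothesis, and no rule prevents the misreading.

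A second reply is that the sample size may be adequate. That is fair. At true difference 0, a margin of 1 at SD 1.5 or of 2 at SD 3 needs 98 patients for 90% power, the same as the difference test. What is missing is the margin and the decision rule, not necessarily patients.

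A third is that 62% is an unfavourable case. This is also fair. As an illustration, take a constant 1-unit deficit averaged over 1, 24 and 48 h, with SDs 3, 1.5 and 1.5. With within-patient correlations of 0.3-0.7 (an assumption; the plan gives none), it would be non-significant in about 9-22% of trials. At SD 1.5 with deficits of 1.5 units or more, non-significance misleads less often (0.1% or below) than the 2.5% that a CI rule allows. But 1 h is a planned assessment, no primary time point is named, and a deficit confined to the early period would not be averaged away so kindly.

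**Conclusion.** The concern holds. The plan's hypothesis has no test that can support it in the situation the hypothesis itself describes.

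The size depends on time point and margin. The problem is large at 1-6 h for deficits of 1-1.5 units (30-62% non-significant, against 2.5% under a CI rule). It is moderate, at 9%, for 2 units at SD 3 or 1 unit at SD 1.5. It is negligible at 24-48 h for larger deficits if the SD really is 1.5. These figures rest on the assumptions listed with the inputs. The logical gap does not depend on them.

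One design feature weakens the inference further. SPGB patients may receive EBP within 48 hours and are analysed as randomised, which could draw the later scores together.

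**What to change.** Before outcome data are examined, choose one of two routes.

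**(a) Make it a non-inferiority trial.** Pre-specify one justified margin from the plan's 1-2 unit range. One unit is the stricter end, though it is still large beside the mean NRS of 1-2 expected at 24-48 h. Pre-specify one contrast from the planned mixed model: a single time point, or an overall contrast across the 48 hours, which would suit the primary aim equally well. Conclude equal effectiveness only if the upper limit of the two-sided 95% CI for SPGB minus EBP is below the margin. State that a non-significant difference is not support, and restate power for this test.

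The cost is wording, one contrast with its CI, and one power sentence. The claim becomes harder to make, and 100 patients suffice only under some assumptions. For 90% power at true difference 0, the total is 98 (margin 1 at SD 1.5, or margin 2 at SD 3), 172 (margin 1 at SD 2, or margin 1.5 at SD 3), 266 (margin 1 at SD 2.5) or 382 (margin 1 at SD 3).

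**(b) Reword.** Bring the hypothesis and exploratory objective into line with the neutral primary objective. The cost is two sentences, and the trial then cannot claim equal effectiveness.

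Under either route, describe the result as comparing strategies that start with SPGB or with EBP, and report repeat procedures of each type by arm and time point. Repeat procedures are already to be collected; make explicit that their timing is recorded, since the wording in Study Design/Methods leaves this unclear.

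### The secondary aim compares known with unknown puncture under SPGB alone, which mixes prognosis with treatment effect; a two-arm treatment-by-puncture-type interaction would separate them

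*Combined protocol and SAP*

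**What the plan says.** The Specific Secondary Aim (Synopsis, Aims) is to "Compare the effectiveness of a sphenopalatine ganglion block in known versus unknown dural puncture for postdural puncture headache relief". The two sides of the comparison are puncture types, and SPGB is the only treatment mentioned.

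The Secondary Objective in the same Synopsis is wider: "Evaluate effectiveness of sphenopalatine ganglion block and epidural blood patch for known and unknown dural puncture in postpartum parturients with PDPH". It brings in EBP but does not say that the two treatments are to be compared within, or across, puncture types.

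Under Study Design/Methods, only treatment is allocated at random: "Each study participant will be randomized to receive either an EBP or a SPGB". No stratification by puncture type is mentioned. The data to be collected include "details and timing of the original neuraxial procedure", but known and unknown puncture are not defined.

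The only efficacy model in Statistical Methods concerns treatment over time: "These mean values between the 2 treatment groups over time will be tested for statistical significance using a longitudinal mixed linear model". It has no puncture-type term, interaction or subgroup analysis. The sample size likewise addresses the treatment comparison alone: "Assuming that we wish to detect a 1-2 unit difference in the NRS between the 2 treatment groups as being clinically meaningful".

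**The concern.** Whether a puncture was known or unknown is a characteristic that the patient brings to the trial. If headache severity or recovery differs by puncture type whatever treatment is given, SPGB patients with one type will do better than those with the other even when SPGB works equally well in both. A comparison inside the SPGB arm cannot tell these situations apart. That the patients come from a randomised trial does not help, because randomisation did not assign the factor being compared.

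The EBP arm supplies what is missing. Any prognostic difference common to both arms cancels when the SPGB-EBP difference in known punctures is set against the SPGB-EBP difference in unknown punctures.

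At stake is the trial's only stated secondary aim. Followed as written, it could lead to a published statement that SPGB suits one kind of puncture better when the SPGB-EBP difference is the same in both. Because aim and objective differ and no analysis is specified, the contrast could also be chosen after the data are seen. The primary comparison is not affected.

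**Working it through.** **Inputs from Statistical Methods.** 50 patients per arm; SD 3 at 1-6 h and 1.5 at 24-48 h after treatment; a difference of interest of 1-2 NRS units; 90% power.

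**Assumptions, because the documents give no figure.** Two-sided alpha 0.05; a known/unknown split of 25/25 per arm (35/15 and 40/10 as variants); a prognostic gap of 1 or 2 units between puncture types, equal in both arms; no true interaction; one time point, without baseline adjustment.

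**Step 1: the plan's own figure.** n per arm = 2(1.96 + 1.28)² × (SD/difference)². A difference of 1 with SD 1.5, or 2 with SD 3, gives 47.3, so 48 per arm against the stated 50. Power at 50 per arm is 91.5%. The sample size therefore reproduces, but for the main treatment comparison only. No figure is stated for the secondary aim.

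**Step 2: standard errors.**
- Within SPGB: SE = SD × √(1/25 + 1/25). At SD 1.5 this is 0.424; the 95% half-width is 2.011 × 0.424 = 0.85 (t, 48 df).
- Interaction: SE = SD × √(4/25). At SD 1.5 this is 0.600; the half-width is 1.985 × 0.600 = 1.19 (t, 96 df).
- At SD 3 the half-widths double, to 1.71 and 2.38.

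**Step 3: how often each test is significant when the gap is prognostic only.** The within-SPGB figures are t-test powers. The interaction figures come from 20,000 simulated trials with 25 per cell.

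| SD | Gap (units) | Within-SPGB test, 25/25 | Interaction test |
|---|---|---|---|
| 1.5 | 1 | 64% | 5.2% |
| 1.5 | 2 | over 99% | 4.9% |
| 3 | 1 | 21% | 4.8% |
| 3 | 2 | 64% | 5.0% |

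For a 1-unit gap at SD 1.5, uneven splits lower the within-SPGB figure to 56% (35/15) and 46% (40/10).

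**Step 4: what the interaction can detect.** Power ≈ Φ(difference/SE − 1.96), with an even split.
- SD 1.5: Φ(1/0.600 − 1.96) = 38.5% for 1 unit (38% with the t distribution) and 91.5% for 2 units.
- SD 3: Φ(1/1.20 − 1.96) = 13.0% for 1 unit and 38.5% for 2 units.
- With a 40/10 split, power for 1 unit is 26.5% (SD 1.5) or 9.8% (SD 3).
- 90% power for a 1-unit interaction at SD 1.5 needs about 379 patients, roughly four times the 96 that suffice for a main effect of that size.

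**Step 5: the role of time.** Statistical Methods lists NRS at baseline as well as at 1, 24 and 48 h. If baseline is modelled as an outcome, a treatment-by-puncture term without time averages over four visits, and no treatment effect can exist at the first. A constant post-treatment interaction d is then estimated as (0 + d + d + d)/4 = 0.75d.

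**The case against.** The strongest reply is that no within-SPGB test is actually written down. That reading comes from one sentence of the Aims, and the Secondary Objective names EBP as well. This stands in part. A reader might infer that the EBP arm is shut out of the secondary analysis; the documents do not support that, since the objective includes it and nothing forbids a two-arm analysis. But the objective states no contrast between treatments, and the model contains no term that would supply one.

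Second, how SPGB patients with known and unknown punctures fare is a fair descriptive question. That also stands, and such a comparison can be kept if it is labelled descriptive. The aim, however, is worded as a comparison of effectiveness.

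Third, the 64% is the power to detect a real difference that the illustration builds in, and becomes an error only when that difference is read as one in treatment effect. This is correct. The figure also depends on an assumed split and gap, and falls to 21% if the gap stays at 1 unit with SD 3. Using baseline NRS would partly remove a gap already present at baseline, but not a difference in rate of recovery.

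Finally, a reader might infer that the inclusion criterion "Dural puncture has been performed" excludes unknown punctures. It does not: the criterion does not require the puncture to have been recognised at the time, so an unrecognised one satisfies it.

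**Conclusion.** The point holds as a matter of analysis choice. On its plain reading, the secondary aim is a non-randomised comparison within one arm, it does not match the objective, and no planned analysis serves either wording. Under the stated assumptions the within-SPGB test would be significant in 21% to over 99% of trials at an even split with no difference in treatment effect between puncture types, against about 5% for the interaction. The documents do not show that prognosis differs by puncture type; the size of the problem depends on that gap, the direction of the argument does not.

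The interaction has limits too. It removes only prognosis common to both arms, and an interaction found would still be an association with puncture type rather than proof that puncture type causes it. With 100 patients it is an exploratory estimate. This is a cheap improvement that leaves the primary analysis untouched.

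**What to change.** 1. Reconcile aim and objective, for example: *Compare the SPGB-EBP difference in NRS between known and unknown dural puncture.*
2. Define known and unknown from the neuraxial procedure record, fixed before randomisation.
3. In the mixed model for 1, 24 and 48 h, use baseline NRS as a covariate and add puncture type, treatment × puncture type, and their interactions with time. If baseline is kept as an outcome, test treatment × puncture type × time instead.
4. Report the SPGB-EBP difference with 95% CI within each puncture type, and the interaction with its CI, all labelled exploratory. Any known-versus-unknown comparison within SPGB is descriptive only.

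Inclusion criterion 2b needs no change.

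**Cost.** A reworded aim, a definition and a few model terms, with no extra patients or visits. Details of the neuraxial procedure are already to be collected, though it should be confirmed that they are enough to classify puncture type. The price is precision: a half-width of about 1.19 instead of 0.85 units at SD 1.5, and power of about 38% (SD 1.5) or 13% (SD 3) for a 1-unit interaction with an even split. After failure within 48 h, "the participant will be offered another SPGB or an EBP if in the SPGB arm or simply another EBP if in the EBP arm"; EBP given to SPGB patients may dilute the 24 h and 48 h contrasts under intention-to-treat, and the report should say so.

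### Only failed SPGB patients can cross to the comparator within 48 hours, so the 24 and 48 hour intention-to-treat result compares two treat-and-retreat strategies and cannot by itself show that SPGB is as effective as EBP

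*Combined protocol and SAP*

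**What the plan says.** **Retreatment (Study Design/Methods).** Patients are randomised to SPGB or EBP. The retreatment rule applies "if the SPGB or EBP fails initially or subsequent failure within the 48 hour time period", and then "the participant will be offered another SPGB or an EBP if in the SPGB arm or simply another EBP if in the EBP arm". Procedures are capped at two, without saying whether that means two in total or two of each kind. Repeat procedures within 48 hours are collected as data. NRS is recorded at 1, 24 and 48 hours after the procedure; which procedure starts the clock is not stated.

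**Analysis (Statistical Methods).** "The primary statistical analysis will be by intention-to-treat", using a longitudinal mixed linear model for mean NRS. Retreatment does not appear there as an outcome, a model term, an event with a handling rule or a sensitivity analysis. A CONSORT diagram tracing patients after randomisation is promised, but it does not name retreatment.

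**Conclusion sought.** The Hypothesis reads "Sphenopalatine Ganglion Block is as effective as epidural blood patch for relieving post-dural puncture headache pain". Expected Outcomes says "we will be able to determine the effectiveness of SPGB for the treatment of PDPH when compared to EBP placement", and adds that if SPGB is effective, "this could change the management and algorithm in the treatment of PDPH for postpartum parturients".

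**Expected failure (Risks to Patients).** For SPGB: "Common risk is failure to relieve symptoms". For EBP: "Rare risks include bleeding, infection, nerve damage, paralysis, dural puncture, no relief of symptoms".

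**The concern.** Intention-to-treat keeps every score in the randomised arm, including scores taken after a patient in the SPGB arm has had an EBP. Relief produced by that EBP counts towards the SPGB arm. Nothing in the EBP arm corresponds to this, because a failed EBP leads only to another EBP. The 1 hour score is affected too if retreatment comes before it, since an initial failure has no time attached.

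The stake is the conclusion. If EBP is truly better, rescue EBP pulls the arms together, which is the direction the hypothesis favours. No margin is stated for the claim of equal effectiveness, so a small, non-significant difference at 24 to 48 hours could be read as support for SPGB itself. The data needed to separate the first procedure from its rescue, namely the time of the repeat and the pain score just before it, may not be recoverable afterwards.

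**Working it through.** **1. What each arm can receive within 48 hours**

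| Arm | First procedure | After failure | Can receive the comparator? |
|---|---|---|---|
| SPGB | SPGB | SPGB or EBP | Yes |
| EBP | EBP | EBP | No |

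This asymmetry, with an analysis that ignores retreatment, fixes what is estimated at 24 and 48 hours. It needs no rate.

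**2. The plan's own figure.** From Statistical Methods: 50 per arm, 90% power, a 1 to 2 unit difference, SD 1.5 at 24 to 48 hours. Two-sided 0.05 is assumed, because no alpha is stated.
- n per arm = 2 × (1.960 + 1.282)² × 1.5² / 1² = 47.3, so 48; the t-test version gives 49, or 98 in total against about 100.
- SE = 1.5 × √(2/50) = 0.30. Noncentral t power (98 df) for 1 unit is 0.910.

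The stated size and power are reproduced with no term for crossover.

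**3. Random crossover (assumed shares).** If a share c of the SPGB arm takes on the EBP mean, the observed difference is 1 × (1 − c).

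| c | Difference | Power |
|---|---|---|
| 0 | 1.0 | 0.910 |
| 10% | 0.9 | 0.844 |
| 20% | 0.8 | 0.752 |
| 30% | 0.7 | 0.637 |

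**4. Both arms retreated above one pain threshold (simulation).** EBP scores are N(m, 1.5) and SPGB scores N(m + 1, 1.5). The threshold is m + 1 + 1.5 × z(1 − f), so that f = 10/20/30% of the SPGB arm exceeds it; 2.6/6.6/11.7% of the EBP arm then does. Patients above it get a second score, at the EBP mean if treated with EBP and at the SPGB mean if SPGB is repeated. The assumed within-patient correlation is 0.5.

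| SPGB failures taking EBP | Difference at f = 10/20/30% | Power |
|---|---|---|
| None | 0.91 / 0.89 / 0.89 | 90 / 90 / 90% |
| Half | 0.86 / 0.79 / 0.74 | 87 / 83 / 79% |
| All | 0.81 / 0.69 / 0.59 | 84 / 74 / about 62% |

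The fall from the first row to the others is the part due to crossover. With independent second scores the three power rows are 86/85/86%, 81/73/69% and 75/60/47%.

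**5. Boundary checks**
- Equal treatments, same rule in both arms: difference 0, rejection rate 5%.
- True difference of 2 units: the lowest power in any crossover case is 94% (all take EBP, independent scores, f = 30%).
- Scale floor: cutting scores off at 0 or 1, with EBP mean 1 or 2, lowers the crossover figures by about 0 to 21 points. The largest falls are in the last row of the table above, to about 73/58/42% with EBP mean 1 and floor 1. Power without retreatment becomes 85 to 91%.
- Implied thresholds: the plan's 24 to 48 hour mean of 1 to 2, plus 1 unit, gives an SPGB mean of 2 to 3. The thresholds are then NRS above 3.9 to 4.9 (10%), 3.3 to 4.3 (20%) and 2.8 to 3.8 (30%).

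**The case against.** The best defence is that nothing here is wrong. Rescue is part of care, intention-to-treat is the right primary analysis, and an aim of comparing effectiveness over 48 hours in randomised patients can be read as a comparison of treatment policies. The remark about the treatment algorithm fits that reading. Repeat procedures are recorded, and the promised CONSORT diagram could show them. All of this stands. A reader might infer that the intention-to-treat analysis is invalid; the documents do not support that. What remains is that the plan never names the strategies as its target, while the Hypothesis and Expected Outcomes speak of SPGB itself.

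The power figures can also be challenged, fairly:
- The plan does not say whether its 1 to 2 units is a difference before or after retreatment. If after, no further dilution applies.
- The calculation is a single 24 to 48 hour t-test; the planned mixed model also uses the 1 hour score and may behave differently.
- The 20 to 30% shares mean retreating at NRS above about 3 to 4. With an SPGB mean of 2 to 3 and SD 1.5, only about 2 to 9% exceed 5. Early failures, when the plan expects 3 to 4 ± 3, are not modelled.

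A reader might therefore infer too much in saying that the trial is underpowered; without a retreatment rate that cannot be shown. Nor do the risk lists show that EBP is better. They are side-effect wording without rates, and only make some crossover plausible.

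**Conclusion.** The point holds as a mismatch between what the 24 and 48 hour analysis estimates and what the plan intends to conclude, and that part rests on the text alone. The distortion is conditional: it favours the SPGB hypothesis if EBP is truly better, and is absent if the treatments are equal and retreated by the same rule. A reader might infer that the trial is biased towards SPGB whatever the truth; the equal-treatments check rules that out.

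The size is hypothetical. For a true 1-unit difference before retreatment, power could drop from 91% to between 84% and about 62% when 10 to 30% of SPGB patients are retreated and all of them take EBP, at correlation 0.5 and ignoring the scale floor. The loss is smaller if only half cross, and larger with independent second scores or a floor. At 2 units it matters little. This is a cheap improvement, not a flaw that invalidates the design.

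**What to change.** Care stays as it is; only wording, recording and analysis change.

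1. Keep intention-to-treat as primary, but word the 24 and 48 hour hypothesis and conclusion as a comparison of the two strategies. Do not claim from this result alone that SPGB itself is as effective as EBP.
2. Count 1, 24 and 48 hours from the first procedure.
3. Record the time of any repeat or crossover procedure, and the NRS immediately before it.
4. Pre-specify one supporting analysis of the first procedure alone: relief at 48 hours, with the NRS cut-off stated in advance, and no repeat procedure of either kind. Any repeat counts as failure in both arms.
5. Within the CONSORT disposition already promised, make explicit the proportion retreated in each arm and the proportion of SPGB patients who cross to EBP.
6. State that the 90% power makes no allowance for crossover.

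The cost is one time stamp, one extra NRS reading, one extra analysis and some wording. The supporting analysis has limits: it depends on a failure that the plan does not define and on retreatment decisions by people who know the treatment. It is also imprecise. As a guide, for the proportion free of retreatment alone, the 95% half-width is 1.96 × √(p₁q₁/50 + p₂q₂/50). That gives about ±9 points at 0.90 versus 0.974, ±13 at 0.80 versus 0.934 and ±16 at 0.70 versus 0.883; the relief endpoint in item 4 will have its own width. It should therefore support the intention-to-treat result and not replace it.
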